4.6 Criteria for Premature Withdrawal

Subjects have the right to withdraw from the study at any time for any reason.

In the case that the subject decides to prematurely discontinue study treatment [“refuses treatment”], he/she should be asked if he/she can still be contacted for further information. The outcome of that discussion should be documented in both the medical records and in the eCRF. If lost to follow-up, the investigator should contact the subject or a responsible relative by telephone followed by registered mail or through a personal visit to establish as completely as possible the reason for the withdrawal. A complete final evaluation at the time of the subject’s withdrawal should be made with an explanation of why the subject is withdrawing from the study.

When applicable, subjects should be informed of circumstances under which their participation may be terminated by the investigator without the subject’s consent. The investigator may withdraw subjects from the study in the event of intercurrent illness, adverse events, treatment failure after a prescribed procedure, lack of compliance with the study and/or study procedures (e.g., dosing instructions, study visits), cure or any reason where it is felt by the investigator that it is in the best interest of the subject to be terminated from the study. Any administrative or other reasons for withdrawal must be documented and explained to the subject.

If the reason for removal of a subject from the study is an Adverse Event, the Adverse Event will be recorded on the eCRF. The subject should be followed until the Adverse Event has resolved, if possible.

An excessive rate of withdrawals can render the study non-interpretable; therefore, unnecessary withdrawal of subjects should be avoided. Should a subject decide to withdraw, all efforts will be made to complete and report the observations prior to withdrawal as thoroughly as possible.

4.7 Replacement Policy (Ensuring Adequate Numbers of Evaluable Subjects)

For Patients

No subject prematurely discontinued from the study, for any reason, after receiving at least a single dose of treatment, will be replaced.

For Centres

A centre may be replaced for the following administrative reasons:

Excessively slow recruitment.

Poor protocol adherence.

5. SCHEDULE OF ASSESSMENTS AND PROCEDURES

The complete schedule of assessments is tabled in the synopsis of protocol (see Schedule of Assessments, page 10).

5.1 Screening Examination and Eligibility Screening Form

All subjects must provide written informed consent before any study specific assessments or procedures are performed.

A screening examination should be performed 21 days before study enrolment. Patients who fulfil all the inclusion and none of the exclusion criteria will be accepted into the study.

An Eligibility Screening Form (ESF) documenting the investigator's assessment of each screened subject with regard to the protocol's inclusion and exclusion criteria is to be completed by the investigator.

A screen failure log must be maintained by the investigator.

5.2 Procedures for Enrolment of Eligible Patients

Once a patient has fulfilled the entry criteria, will be enrolled in the study, beginning with the EGFR mutation testing at the Central Laboratory [REDACTED] by Sequential Technique. A surgical fragment or biopsy formalin-fixed, paraffin-embedded or a tumour material obtained through aspiration cytology fixed and paraffin-embedded in a cell-block, must be sent to the Central Laboratory [REDACTED]. If activating mutations (exons 19 and 21 mutations) in the TK domain of EGFR gene are identified, patients are eligible to participate in the study. Although, for methodological issues, mutations will be identified from the exon 18 to 21, but only patients with Exon 19 deletion or exon 21 substitution L858R in the TK domain of EGFR gene will be enrolled in this trial.

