END OF STUDY	The study will end when the last patient has stopped erlotinib therapy and completed their last safety follow-up visit (28 days after last study drug administration). For all patients who have discontinued study drug treatment and are alive, information on survival will be collected.
INVESTIGATIONAL MEDICAL PRODUCT(S) DOSE/ ROUTE/ REGIMEN	Patients will be dosed daily with 150 mg erlotinib taken orally until disease progression or unacceptable toxicity. Dose reduction will be allowed according to protocol (Section 6.)
ASSESSMENTS OF:	
- EFFICACY	
Primary endpoint:
 
 • Objective Response Rate (ORR). 
Secondary endpoints:
 
 • Progression Free Survival, • Overall Survival (OS), • Safety profile, • EGFR mutation frequency, • Response duration (RD).
- SAFETY	All evaluations will be performed accordingly with the Schedule of Assessments. If clinically indicated, more evaluations could be performed. All adverse events (AEs) will be assessed using the National Cancer Institute Common Terminology Criteria for AEs (NCI CTC-AE) version 4.0. The incidence of serious adverse events (SAEs) and non-SAEs related to

- erlotinib therapy will be determined. Additional information about AEs of special interest (serious and non-serious) such as Stevens-Johnson syndrome and interstitial lung disease (IDL)-like events will be collected. Information about laboratory exams (haematology, biochemistry and coagulation), ECG and physical examination will be also collected.
- EGFR Mutation analysis If patients are deemed eligible to participate in the study by the investigator, a surgical fragment or biopsy formalin-fixed, paraffin-embedded or a tumour material obtained through aspiration cytology fixed and paraffin-embedded in a cell-block, must be sent to the Central Laboratory [REDACTED]. If activating mutations (exons 19 and/or 21 mutations) in the TK domain of EGFR gene are identified, patients are eligible to participate in the study.
-

PROCEDURES (summary):

The following examinations will be made as scheduled in the attached table:

- After the signature of the patient informed consent form, the EGFR mutation testing will be performed at the Central Laboratory [REDACTED] by Sequencing Technique.

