A recent phase III study (OPTIMAL) of first line treatment with erlotinib compared to platinum-based chemotherapy (gemcitabine/carboplatine), in Asian population with NSCLC with EGFR mutation has shown a median PFS of 13.1 months in the erlotinib arm with HR=0.16 (95% CI; 0.10-0.26) versus 4.6 months in the chemotherapy arm. It has also shown an ORR of 82.9% in the erlotinib arm versus 36% in the chemotherapy arm (p<0.0001)²⁵. Erlotinib should therefore be considered in preference to first line chemotherapy in patients with this distinct disease.

Considering the potential benefit for patients in initiating erlotinib earlier in their treatment it becomes crucial to evaluate its anti-tumoral activity through a more sensitive and accurate endpoint such as objective response rate during first-line treatment in Caucasian populations.

In this trial erlotinib will be given in first-line treatment for advanced NSCLC with EGFR mutation positive.

Although this trial is a non-randomized phase II trial, Erlotinib is currently used in clinical practice to treat NSCLC²⁶. Any patient with locally advanced or metastatic non-small cell lung cancer disease found to have an EGFR exon 19 deletion or exon 21 mutations will be offered first-line treatment with erlotinib having ORR as primary efficacy endpoint.

EGFR mutations rates in Portugal

Previous studies with gefitinib have shown the incidence of mutations to be around 8% in unselected patients, whereas studies conducted in Asia show mutation rates of 19-60% In the Spanish Lung Cancer Group study of erlotinib that included only Spanish patients with EGFR mutations the EGFR mutation rate was 16.6%. In this trial, the population was mainly female, non-smokers and adenocarcinoma. The EGFR mutation's rate amongst

NSCLC patients, in Portugal is currently unknown so that the health burden and economic implications of treatments directed specifically at patients with this characteristic cannot be accurately assessed.

Therefore one of the objectives of the current study is to assess the EGFR mutation rate in Portugal NSCLC population. This will be done by testing Portuguese patients newly diagnosed with recurrent or metastatic NSCLC for the EGFR mutations.

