5.3 Clinical Assessments and Procedures

Testing for EGFR mutation will be performed only at Screening. All of the other clinical and safety assessments will be performed at Screening, Baseline and on Day 1 of every 8th week until PD, death, or unacceptable toxicity, as indicated in the Schedule of Assessments. For all patients who have discontinued study drug treatment and are alive, information on further therapy for NSCLC and survival will be collected.

Tumor Response Criteria

Tumor response will be evaluated according to the RECIST criteria (Eisenhauer et al., 2009) (see Appendix 1).

In this study, tumour response will be measured using computer tomography (CT) or magnetic resonance image (MRI) scans of the chest and upper abdomen, for imaging of liver and adrenal glands. Patients known to have bone metastasis or displaying clinical or laboratory signs (e.g. serum alkaline phosphatase (ALP) > 1.5 ULN) of bone metastasis should have an isotope bone scan at baseline. In cases where there are suspected brain metastases, CT scanning of the brain will be performed.

Post-baseline assessments are to be performed within +/- 5 days for the 8 weekly assessments. If there is suspicion of disease progression based on clinical or laboratory findings, a tumour assessment should be performed as soon as possible, before the next scheduled evaluation.

Consistency of consecutive CT-scans, X-rays or MRIs should be ensured during all assessments for each patient, with the same technique being used for evaluating lesions throughout the treatment period. The use of spiral CT or MRI is required for baseline lesions of < 20 millimetres (mm) and must be documented in medical records and used consistently throughout the study. The use of oral and IV contrast etc. should, as long as it is clinically possible, be kept consistent. Tumor measurements should be made by the same investigator/radiologist for each patient during the study to the extent that this is feasible.

Scheduling of tumour assessments

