### **5.3.9.2 Secondary Efficacy Endpoints**

The secondary efficacy variables include:

- Progression-free survival (PFS), defined as the time from baseline visit to the date of first occurrence of disease progression or death for any cause while the patient was under study or during the prolonged follow-up period. PFS will be summarized as median time and will be estimated using the Kaplan-Meier method. Ninety five percent (95%) confidence interval will be estimated for median time to PFS.
  
- Overall survival (OS), defined as the time from the first dose of erlotinib to the date of death due to any cause while the patient was under study or during the prolonged follow-up period. Overall survival variable will be summarized as median time to OS and will be estimated using the Kaplan-Meier method. 95% confidence interval will be estimated for median time to OS. The date of first dose is not captured in the study CRF. Therefore, for this endpoint it will be assumed that the patient will take the first dose at the day of the baseline visit.
  
- Epidermal growth factor receptor (EGFR) mutation frequency. The presence of EGFR mutation (exon 19 deletion and/or exon 21 substitution L858R) in the study population will be presented as the relative frequency of those mutations among the total screened patients. A 95% confidence interval will be estimated for this value using binomial distribution.
  
- Response duration, defined as the time of initial response (CR/PR whichever is first recorded) until documented tumor progression. Response duration will be summarized as median time and will be estimated using the Kaplan-Meier method. Ninety five percent (95%) confidence interval will be estimated for median time to response duration.

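### The rationale promises the EGFR mutation rate of the Portuguese NSCLC population, but the testing order and the SAP denominator are not designed to estimate it

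*Protocol*

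**What the plan says.** **The aim.** Protocol 1.3, under the paragraph on mutation rates in Portugal, notes that the national rate is unknown and that burden and cost therefore cannot be assessed. It continues: "Therefore one of the objectives of the current study is to assess the EGFR mutation rate in Portugal NSCLC population". The means is given as "testing Portuguese patients newly diagnosed with recurrent or metastatic NSCLC for the EGFR mutations". The formal secondary objective in Protocol 2.2 is narrower: the mutation frequency in the study population.

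**Who is tested.** Protocol 5.2 says: "Once a patient has fulfilled the entry criteria, will be enrolled in the study, beginning with the EGFR mutation testing". The synopsis paragraph on mutation analysis agrees: "If patients are deemed eligible to participate in the study by the investigator, a surgical fragment or biopsy" and so on must go to the central laboratory. The synopsis list of procedures sets a different condition: "After the signature of the patient informed consent form, the EGFR mutation testing will be performed". Protocol 5.3 adds only the timing: "Testing for EGFR mutation will be performed only at Screening".

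**What is divided by what.** SAP 5.3.9.2 defines the endpoint as the "relative frequency of those mutations among the total screened patients", with a 95% binomial confidence interval. SAP Table 16 is headed as covering all patients and has a yes/no row for whether the EGFR test was done, so it foresees screened patients without a test.

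Neither document requires consecutive patients to be offered testing, and neither adjusts the frequency for who was tested.

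**The concern.** A mutation rate meant to support health-burden and economic estimates needs a defined source population and a known route from that population to the test. Here the rationale names one population, the enrolment section tests a subset of it, and the SAP denominator may be a third group.

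The filter is not trivial. Read with Protocol 4.2 and 4.3, the tested group must have measurable disease, adequate organ function and a minimum life expectancy. It must be free of symptomatic brain metastases, most other neoplasms, coumarin use and parenchymal lung disease, including lymphangitic spread. Selection can also occur before that point, because investigators choose whom to approach.

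At stake is the interpretation of a named secondary endpoint that also forms part of the interim epidemiological description. A reader could take the published percentage and its interval as a national figure.

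**Working it through.** **1. The plan's own figure.** Inputs from Protocol 8.2.6: prevalence p = 0.10, 30 positives wanted, 95% confidence. The number to test is the smallest n for which the lower two-sided normal limit of the expected positives, n·p − 1.96·√(n·p·(1−p)), reaches 30.
- n = 420: 42 − 1.96·√37.8 = 29.95
- n = 421: 42.1 − 1.96·√37.89 = 30.04

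The stated 420 is therefore reproduced to within one patient. Protocol 8.2.6 calls these patients enrolled for testing; SAP 5.1 calls the same 420 screened. The two agree only if everyone screened is tested.

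**2. What the interval covers.** At 420 tested and 10%, the half-width is 1.96·√(0.1·0.9/420) = 0.0287, or 2.9 points. The exact interval for 42/420 is 7.3% to 13.3%. Both reflect sampling error alone.

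**3. The population implied by each place.**

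| Place | Group implied |
|---|---|
| Protocol 1.3 | Newly diagnosed recurrent or metastatic NSCLC, no other restriction |
| Protocol 5.2; synopsis, mutation analysis | Patients already judged eligible on the other criteria |
| Synopsis, procedures | Consented patients |
| SAP 5.3.9.2 | All screened patients, tested or not |

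Mutation status is itself inclusion criterion 2b, so the entry criteria in Protocol 5.2 can only sensibly mean the remaining ones.

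**4. Effect of the denominator.** Let f be the share of screened patients who are tested, and suppose all screened patients are counted. The documents do not give f, so a range is assumed. A true 10% is reported as 10% × f.

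| f | Reported | Screened to obtain 420 tests (420/f) |
|---|---|---|
| 0.9 | 9% | 467 |
| 0.7 | 7% | 600 |
| 0.5 | 5% | 840 |

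This error is always downward.

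**5. Effect of selection.** Let e be the share of the wider population that is eligible, and r the mutation rate in ineligible patients relative to eligible ones. With 10% among eligible patients, the all-patient rate is 10% × (e + (1−e)·r). Neither e nor r is in the documents. Assumed range: e from 0.5 to 0.9, r from 0.5 to 2.
- e = 0.5, r = 0.5: 7.5% (10% overstates by 2.5 points)
- e = 0.9, r = 0.5: 9.5%
- r = 1, any e: 10% (no bias)
- e = 0.9, r = 2: 11%
- e = 0.5, r = 2: 15% (10% understates by 5 points)

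The same formula holds if e is read as the share tested for any reason. Preferential testing of likely carriers corresponds to r below 1 and pushes the estimate upward.

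**6. The only external contrast in the documents.** Protocol 1.3 cites about 8% in unselected patients and 16.6% in a Spanish study whose population was mainly female, non-smoking and with adenocarcinoma. The gap is 16.6 − 8 = 8.6 points, about three times the half-width in step 2. It comes from different studies, so it shows only that reported rates can differ by more than sampling error.

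**The case against.** The strongest reply is that the formal objective, the endpoint and the analysis text all speak of the study population or of screened patients. The national wording sits in the rationale alone. That is correct, and it limits the point to a conflict between the rationale and the rest of the plan. It does not remove the conflict, because the rationale states the aim as an objective and says how it will be met.

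Second, the order of testing is not fixed unambiguously. One synopsis line needs only consent, and the schedule places the test in the same screening column as the other assessments. This stands, and it means the order must be reconciled.

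Third, SAP 5.4 omits missing values individually, which could be read as dropping untested patients from the denominator. That contradicts the wording of SAP 5.3.9.2, and nothing says which rule governs. The downward error in step 4 is therefore conditional.

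Fourth, the plan keeps an eligibility form for each screened patient and a screen failure log (Protocol 5.1), and Protocol 3.3 promises mutation incidence by subgroup at the interim. This helps only in part. A screen failure log does not list patients never offered testing. The SAP presents demographics and diagnosis for the ITT population only, and Table 16 has no subgroup breakdown.

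Several stronger readings are tempting but unsupported:
- *The trial cannot give the national rate.* It would, if eligibility and the choice of whom to test were unrelated to mutation status and the denominator were tested patients. The documents neither claim nor check this.
- *The planned frequency is simply that of trial-eligible patients.* The SAP denominator contradicts this.
- *Selection will roughly double the rate.* The 8% and 16.6% reflect another selection mechanism; sex, smoking and histological subtype are not entry criteria here.
- *Testing last forces about 420 full work-ups instead of about 42.* The schedule puts tumour assessment at baseline, after the mutation result, so the full work-up is not scheduled before the test.
- *Reordering alone would cure the problem.* Favouring likely carriers arises from non-consecutive recruitment, whatever the order.

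**Conclusion.** The point holds as a mismatch between a stated aim and the design. Followed as written, the plan yields a frequency whose source population is undefined and whose interval expresses sampling error only (about ±2.9 points at 420 tested and 10%). Bias may run either way: downward if untested patients are counted (10% becomes 7% at 70% tested), upward if likely carriers are favoured. The scenarios in steps 4 and 5 rest on assumed shares and rate ratios; the documents supply neither, so no bias can be quantified for this trial. Preferential testing is a foreseeable risk, not a documented fact.

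No number in the plan is wrong because of this, the 420 is reproduced, and the ORR analysis is unaffected. It should be corrected because it changes what may be concluded from a secondary endpoint.

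**What to change.** 1. Reconcile Protocol 1.3, Protocol 5.2, both synopsis statements and SAP 5.3.9.2 to one target population and one order of testing.
2. In Protocol 1.3 and in the reports, describe the result as the *frequency among trial-eligible patients tested at the participating centres*, and drop the national-rate claim.
3. In SAP 5.3.9.2 and Table 16, make patients with a valid EGFR result the denominator, and report the number and characteristics of screened patients who were not tested.

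These changes cost wording and a modest revision of one table; they need no additional patients or tests.

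If recruitment is still open and the national aim is to be kept, an alternative is to test consecutive consented newly diagnosed patients at each centre before the other criteria are applied, with a log of those not offered testing. That would need protocol and consent changes and somewhat more EGFR tests, since some positives will fail other criteria. It is a design option open to debate; the rewording is the minimum.

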5.3 Clinical Assessments and Procedures

Testing for EGFR mutation will be performed only at Screening. All of the other clinical and safety assessments will be performed at Screening, Baseline and on Day 1 of every 8th week until PD, death, or unacceptable toxicity, as indicated in the Schedule of Assessments. For all patients who have discontinued study drug treatment and are alive, information on further therapy for NSCLC and survival will be collected.

Tumor Response Criteria

Tumor response will be evaluated according to the RECIST criteria (Eisenhauer et al., 2009) (see Appendix 1).

In this study, tumour response will be measured using computer tomography (CT) or magnetic resonance image (MRI) scans of the chest and upper abdomen, for imaging of liver and adrenal glands. Patients known to have bone metastasis or displaying clinical or laboratory signs (e.g. serum alkaline phosphatase (ALP) > 1.5 ULN) of bone metastasis should have an isotope bone scan at baseline. In cases where there are suspected brain metastases, CT scanning of the brain will be performed.

Post-baseline assessments are to be performed within +/- 5 days for the 8 weekly assessments. If there is suspicion of disease progression based on clinical or laboratory findings, a tumour assessment should be performed as soon as possible, before the next scheduled evaluation.

Consistency of consecutive CT-scans, X-rays or MRIs should be ensured during all assessments for each patient, with the same technique being used for evaluating lesions throughout the treatment period. The use of spiral CT or MRI is required for baseline lesions of < 20 millimetres (mm) and must be documented in medical records and used consistently throughout the study. The use of oral and IV contrast etc. should, as long as it is clinically possible, be kept consistent. Tumor measurements should be made by the same investigator/radiologist for each patient during the study to the extent that this is feasible.

Scheduling of tumour assessments

In this study, assessment of tumour progression during treatment with erlotinib will be performed every 8th week during the study visits and on the End of Study visit (as given in the Schedule of Assessments). Baseline tumour assessment must be performed within 21 days before first dose of study drug treatment. Post-baseline assessments are to be performed +/- 5 days for the 8 weekly assessments. If there is suspicion of disease progression based on clinical or laboratory findings before the next scheduled assessment, an unscheduled assessment should be performed.

If a subject inadvertently misses a prescribed tumour evaluation or a technical error prevents the evaluation, the subject may continue treatment until the next scheduled assessment, unless signs of clinical progression are present.

ECOG Performance Status

Performance Status (PS) will be measured using the ECOG performance scale (see Appendix 2), at screening, baseline, at each study visit on Day 1 of every 8th week of treatment period, and at the safety follow-up visit (28 days after the last study drug administration).

It is recommended, where possible, that a subject's PS will be assessed by the same person throughout the study.

Clinical Safety Assessments

The NCI CTC-AE version 4.0 will be used to evaluate the clinical safety parameters of the study drug. Patients will be assessed for adverse events at each clinical visit from screening onwards and as necessary throughout the study.

A complete medical history (including demographics) will be performed at screening and a physical examination will be performed at each visit, as indicated in the Schedule of Assessments.

Safety assessments will consist of monitoring and recording all AEs and serious adverse events (SAEs); regular monitoring of haematology, biochemical analyses results and physical examinations. Electrocardiogram (ECG) recordings will be performed as part of the screening (baseline) assessments and if clinically indicated throughout the study.

